3.4 Secondary Endpoints

- 1. Maternal safety defined as
 - Maternal adverse events
 - Pregnancy and delivery outcomes
 - stillbirth or intrauterine fetal demise
 - intrapartum hemorrhage
 - postpartum hemorrhage
 - hypertensive disorders of pregnancy (gestational hypertension, pre-eclampsia with and without severe features, eclampsia)
 - gestational diabetes
 - intrauterine growth restriction
 - cholestasis of pregnancy
 - severe maternal morbidity (defined by CDC¹)
 - maternal admission to the intensive care unit
 - maternal death
 - 2. Neonatal/Infant safety defined as
 - Severe neonatal morbidity admission to neonatal intensive care unit
 - Perinatal preterm (<37 weeks) composite defined as fetal or neonatal death, severe bronchopulmonary dysplasia (grade 3), intraventricular hemorrhage grades III-IV, necrotizing enterocolitis (proven – Bell Stage 2A or greater), periventricular leukomalacia, retinopathy of prematurity stage III-V, or proven sepsis (early or late)
 - Perinatal term (>= 37 weeks) composite defined as fetal or neonatal death, respiratory support, Apgar score ≤ 3 at 5

minutes, hypoxic ischemic encephalopathy, seizure, infection (sepsis or pneumonia), birth trauma, meconium aspiration syndrome, intracranial or subgaleal hemorrhage, or hypotension requiring vasopressor support

- Admission to the neonatal intensive care unit
- Neonatal death
- Major malformations, defined as structural abnormalities with medical, surgical or cosmetic importance
- Weight, length, and head circumference at birth (by exam or chart review), 8 weeks, six months and 12 months
- Neurodevelopmental assessments at 6 months and 12 months by Ages & Stages Questionnaires ®
- 3. Infant HCV RNA PCR viral load at 8 weeks, 6 months and 12 months

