 - Perinatal term (>= 37 weeks) composite defined as fetal or neonatal death, respiratory support, Apgar score ≤ 3 at 5 minutes, hypoxic ischemic encephalopathy, seizure, infection (sepsis or pneumonia), birth trauma, meconium aspiration syndrome, intracranial or subgaleal hemorrhage, or hypotension requiring vasopressor support

- Admission to the neonatal intensive care unit
- Neonatal death
- Major malformations, defined as structural abnormalities with medical, surgical or cosmetic importance
- Weight, length, and head circumference at birth (by exam or chart review), 8 weeks, six months and 12 months
- Neurodevelopmental assessments at 6 months and 12 months by Ages & Stages Questionnaires®
- 3. Infant HCV RNA PCR viral load at 8 weeks, 6 months and 12 months

Table 1: Study Visit Schedule

	Maternal Study Visit	Gestational Age (Weeks + Days)/Timing [†]
V1	Screening	12+0 to 29+6
V2	Enrollment*	20+0 to 30+0
V3	Safety check/Med dispense	4 weeks ± 7 days after treatment start
V4	Safety check/Med dispense	8 weeks ± 7 days after treatment start
V5	End of Treatment	Within 7 days after last dose
	Delivery Visit [^]	
V6/iV	Post-treatment for SVR12	12 weeks ± 4 days after last dose
	Infant Study Visit	Infant Age
V6/iV	Infant Visit 1	8 weeks ± 6 weeks
iV2	Infant Visit 2	6 months ± 1 month
iV3	Infant Visit 3	12 months ± 1 month

[†]These are target windows. If the participant cannot be seen within these windows, she should be seen as soon as possible. A delayed visit will not be considered a protocol deviation.

Screening and Enrollment visits are separate visits and therefore should not occur on the same day.

Ideally, once a participant starts study medication (V2, Enrollment), study visits while on study medication should be scheduled 28 days apart or as close to 28 days as possible.

^{*}Start SOF/VEL and continue for 12 weeks (84 days)

[^]The Delivery Visit may occur before or after V5

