2.5 Rationale for Study Design

There is currently no published experience with SOF/VEL in pregnant women, although there were no effects on fetal development observed in mice, rats and rabbits with doses higher than those given for treatment of hepatitis C in humans in data submitted to the FDA. There are reassuring data from our prior study of treatment of pregnant women with LDV/SOF. Because LDV/SOF is not approved for treatment of genotypes 2 and 3, it is imperative to evaluate a pan-genotypic regimen. In highly-affected areas such as West Virginia, genotypes 2 and 3 constitute up to 30% of cases. In this study, treatment will be initiated during the second trimester, reducing the risk of SOF/VEL exposure during organogenesis, ensuring viral supression and a majority of the treatment is completed by delivery, and thus minimizing the risk of perinatal transmission.

The study will be completed in 8 or 9 visits (6 maternal visits and 3 infant visits) which should easily align with routine prenatal and postpartum visits (Table 1). We plan to screen patients between 12+0 and 29+6 weeks of gestation confirmed by ultrasound (ultrasound will be performed prior to enrollment). HCV RNA level to confirm the patient has active infection will be obtained. Laboratory evaluation of liver function including CBC, PT/INR, hepatic panel, creatinine/eGFR, creatine kinase and lipase will be obtained, to evaluate for renal insufficiency, decompensated cirrhosis and baseline elevations of lipase and creatine kinase. Hepatitis B virus (HBV) antigen will be performed to look for evidence of active HBV infection. Medical history and demographic information will also be collected at screening. If the following inclusion and exclusion criteria are met, then the patient will be enrolled into the study between 20+0 and 30+0 weeks' gestation and initiate a 12-week course of SOF/VEL.

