6 STUDY MEDICATION

6.1 Regimen

Each participant will take a 12-week course (84 consecutive days) of SOF/VEL(400 mg of sofosbuvir and 100 mg of velpatasvir), one tablet by mouth once daily.

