7.4.4 Post-Treatment (SVR12) (V6) Visit

The following procedures will occur at the Post-Treatment (SVR12) visit (V6), which should be scheduled 12 weeks ± 4 days from the last dose of study medication. The V6 visit can occur simultaneously with the 8-week Follow-up Visit for the infant (iV1), as applicable. This is the last scheduled clinic visit specifically for the mother. If an HCV RNA test is not obtained at the V6 visit or abstracted from the medical record

^{**}Laboratory test performed as applicable for participants who deliver at site hospitals.

within the V6 visit window or later, then the participant is NOT evaluable and will be replaced with a new participant.

Table 8: Post Treatment (V6)

Visit 7 (V6) Post Treatment Visit		
Component Procedures		
Administrative and Regulatory	 Review/update locator information Visit questionnaire Provide reimbursement 	
Clinical	 Review/update medical history Review/update concomitant medications Perform modified physical examination Record/update AEs Provide available test results from delivery, as applicable 	
Laboratory	 Collect blood: CBC with platelets and differential Hepatic function panel (AST, ALT, albumin, total and direct bilirubin, alkaline phosphatase) PT/INR Creatinine/eGFR Lipase Creatine kinase HCV RNA viral load* Blood sample for HCV genomic deep sequencing (collected and only used in the case of treatment failure) or stored sample for future use, as applicable. 	

^{*}If the participant does not come to the V6 visit, then the HCV RNA viral load may be abstracted from the medical record if it occurs during the visit window or later. If the HCV RNA is detectable then every effort should be made to have the participant return for a blood sample for HCV genomic deep sequencing.

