7.4.5 Infant Follow-Up Visits (iV1, iV2, iV3)

After delivery, infants will be seen at the following time points:

iV1: 8 weeks ± 6 weeks iV2: 6 months ± 1 month iV3: 12 months ± 1 month

The following procedures will occur at the Infant Follow-Up Visits (iV1, iV2, iV3). If blood sampling is not possible, then the results can be collected from the infant's medical record if available. Results of physical and developmental exams will be shared with the mother, and if necessary, with the infant's routine healthcare

provider. Referrals, for instance for early intervention, will be made as indicated by pediatric study staff.

Table 9: Infant Follow-Up Visits (iV1, iV2, iV3)

Visit iV1, iV2, iV3 Infant Follow-Up Visits			
Component	Component Procedures		
Administrative and Regulatory	 Review/update mother/guardian locator information Review infant demographics (iV1) Sign release(s) for medical records for infant, as applicable Provide reimbursement Schedule next visit (iV2, iV3) Review schedule of infant follow-up visits Protocol adherence counseling 		
Clinical	 Review/update medical history* Document pre-existing conditions (iV1)* Review/update concomitant medications* Record/update AEs Age-appropriate physical examination by pediatrician or designee, including growth assessment (weight, length, and head circumference)*** Developmental Exam (Ages and Stages Questionnaire®); with referrals as indicated Provide available laboratory test results, as applicable 		
Laboratory	 Collect infant blood HCV RNA (iV1, iV2, iV3) HCV genomic deep sequencing (only if HCV RNA is detectable)** 		

^{*}May be collected from the medical record as applicable

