10.4.3 Analysis of Neonatal Safety

Neonatal outcomes will be compared to a historical control group of infants who had perinatal HCV exposure. Differences in frequency of each outcome will be

determined by Fisher's exact test. Further, an adjusted analysis based on the collected maternal factors will be conducted in order to determine if any of the findings were related to treatment with SOF/VEL or due to a confounder using regression methods. In addition, all adverse events will be reported descriptively, noting relationship to the study medication as well as any adverse events grade 3 or 4.

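### The 8-week infant growth endpoint may be measured anywhere from 2 to 14 weeks of age, and the comparison stated for neonatal outcomes neither suits continuous growth measures nor names infant age or sex

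*Protocol*

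**What the plan says.** The endpoint in Protocol section 3.4, repeated in the Protocol Summary, is "Weight, length, and head circumference at birth (by exam or chart review), 8 weeks, six months and 12 months". It appears under neonatal/infant safety, and no standardisation for age or sex is mentioned.

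Section 7.4.5 sets the visit windows: "iV1: 8 weeks ± 6 weeks iV2: 6 months ± 1 month iV3: 12 months ± 1 month". The note under Table 1 calls these windows targets and adds: "A delayed visit will not be considered a protocol deviation". Appendix II heads the first infant visit as month 1 to 3, which is not the same interval as 2 to 14 weeks.

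On the link with the mother's last visit, section 7.4.4 says: "The V6 visit can occur simultaneously with the 8-week Follow-up Visit for the infant (iV1), as applicable". That maternal visit (V6) is one "which should be scheduled 12 weeks ± 4 days from the last dose of study medication". Table 1 gives the post-treatment visit and Infant Visit 1 the same visit code, and section 2.5 counts 8 or 9 visits from 6 maternal and 3 infant visits.

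On analysis, section 10.4.3 begins: "Neonatal outcomes will be compared to a historical control group of infants who had perinatal HCV exposure. Differences in frequency of each outcome will be". The method that this sentence goes on to name is Fisher's exact test. The section then plans an adjusted regression analysis using the maternal factors collected.

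**The concern.** Infants grow quickly in the first three months, so a raw weight at 8 weeks means little unless age at measurement is either nearly constant or accounted for. Here the widest of the three infant windows falls in this early period. When the infant visit is combined with V6, the infant's age depends on when the mother started treatment and when she delivered, not on a target of 8 weeks.

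The stated comparison does not repair this. A continuous measurement has no frequency, and no cut-point is given that would create one. The regression that follows is described in terms of maternal factors.

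Postnatal growth serves secondary objective 2, neonatal safety after exposure in the womb. A difference from the historical infants could come from age at measurement, and a real effect could be lost in the spread that age adds.

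**Working it through.** **1. The window.** From section 7.4.5: 8 − 6 = 2 weeks and 8 + 6 = 14 weeks. Width: 12 weeks × 7 = 84 days. Late visits can extend it.

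**2. Is merging with V6 expected?** Section 2.5: 6 + 3 = 9 visits, and the count falls to 8 only if two are merged. With the shared code in Table 1, merging is anticipated, though section 7.4.4 leaves it optional.

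**3. Infant age when the visits are merged.** Inputs: women are "enrolled into the study between 20+0 and 30+0 weeks" of gestation; "Each participant will take a 12-week course (84 consecutive days) of SOF/VEL"; V6 follows 12 weeks after the last dose. Taking the course as uninterrupted and V6 on target (± 4 days):

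Age at V6 = gestational age at start + 12 + 12 − gestational age at delivery.

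| Start | Delivery 34 wk | Delivery 37 wk | Delivery 40 wk |
|---|---|---|---|
| 20+0 | 10 | 7 | 4 |
| 25+0 | 15 | 12 | 9 |
| 30+0 | 20 | 17 | 14 |

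Age moves week for week with the start date and inversely with gestational age at delivery. Preterm infants are therefore older at V6 for a given start, and some combinations fall outside 2 to 14 weeks.

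As an illustration, assume starts uniform over 20 to 30 weeks, 23% preterm (the rate in section 10.3) spread uniformly over 33 to 37 weeks, and term deliveries triangular over 37 to 41.5 weeks with mode 39.3. The V6 date then falls at a median infant age of 10.7 weeks (95% range about 4.6 to 18.1), with about a third between 6 and 10 weeks. This describes V6 dates, not the dates of infant visits held separately.

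**4. Size of the age effect on weight.** The documents give no growth rate; 20 to 35 g/day is assumed.

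- Across the window: 84 × 20 = 1,680 g to 84 × 35 = 2,940 g, or about 1.7 to 2.9 kg.
- Per week of difference in mean age between cohorts: 7 × 20 = 140 g to 7 × 35 = 245 g, or about 0.14 to 0.25 kg.

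**5. Loss of precision with equal age distributions.** With ages uniform over the window, the SD due to age is 1,680/√12 = 485 g to 2,940/√12 = 849 g. Added to an assumed SD of 500 g at a fixed age, the total is √(500² + 485²) ≈ 697 g to √(500² + 849²) ≈ 985 g.

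**6. False signals with unequal mean ages.** Assume 100 infants per group, ages uniform over a 12-week span in each, no true difference, and an unadjusted two-sided 5% comparison of means. Example with SD 500 g, 30 g/day and a 1-week difference:

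- total SD = √(500² + 2,520²/12) = 883 g
- standard error = 883 × √(2/100) = 124.8 g
- shift in standard errors = 210/124.8 = 1.68
- rejection probability = 39%

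For SD 500 to 700 g and 20 to 35 g/day, rejection is about 21 to 42% for a 1-week difference and 64 to 94% for 2 weeks. The protocol does not plan this exact test; the figures only show how sensitive raw weight is to age.

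**The case against.** The strongest reply is that this is detail for the statistical analysis plan, which is not shown. Section 10.4.3 does not mention growth by name. Its Fisher's test can be read as meant for outcomes that have frequencies, such as the composites, intensive care admission, death and malformations. Regression is already planned. Dates, sex and gestational age can be used at analysis, so nothing prevents a sound comparison. Much of this stands: missing covariate lists or z-score rules would not be a finding alone. What remains is that the protocol itself fixes an 8-week endpoint, a 12-week window for it, and a test for each neonatal outcome, and these do not fit together.

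Three stronger readings are tempting, and the documents do not support them.

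- *That the growth comparison simply reflects age.* Bias needs a difference in mean age from the historical infants. The protocol gives neither their ages at measurement nor whether they have 8-week measurements.
- *That age at the infant visit is tied to treatment start.* Combining it with V6 is permitted, not required, and gestational age at delivery matters just as much.
- *That infants with the longest antenatal exposure are measured youngest.* The course is fixed at 84 days. With delivery at 40+0, every start from 20+0 to 28+0 gives the full course before birth, while age at V6 runs from 4 to 12 weeks. Only starts after 28+0 are cut short, by at most 2 weeks. The protocol plans no exposure-trend analysis either.

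The wide window is also a reasonable practical choice, since visits are meant to align with routine care. That argues for handling age in the analysis, not for narrowing the window.

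**Conclusion.** The point holds in a limited form. The raw 8-week measurements can be taken over an 84-day span of infant age, and the analysis stated for neonatal outcomes neither suits continuous measures nor names infant age or sex. The certain cost is precision. Bias, on the scale of 0.14 to 0.25 kg per week of mean-age difference, is possible but cannot be shown from this document. All weight figures rest on the assumed 20 to 35 g/day; the rejection rates rest further on assumed SDs and group sizes.

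The age problem is mainly at the 8-week point: birth measurements are unaffected by visit timing, and the 6- and 12-month windows are ± 1 month. The mismatch with Fisher's test applies to the continuous growth measures at every time point. Growth is one of several secondary safety endpoints and does not drive the sample size, so neither primary endpoint is touched. The change is still worth making, because it makes the 8-week values interpretable at almost no cost.

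**What to change.** 1. In section 3.4 and the Protocol Summary, define the postnatal growth endpoints as age- and sex-standardised z-scores for weight, length and head circumference at the actual measurement date, corrected for gestational age at birth.
2. In section 10.4.3, limit Fisher's exact test to binary outcomes. Compare growth z-scores with the historical infants by linear regression. Where those infants have no comparable measurement, describe the z-scores against the reference population.
3. Compute age from the date of birth, since section 7.4.3 defines the delivery visit date by staff contact or phone call. Where a measurement is abstracted from the record, use its own date.
4. Align the Appendix II column label with the window in section 7.4.5.

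The cost is wording changes and slightly more analysis work. Sex, gestational age and growth measurements are already collected, so no visits or data are added.

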4 STUDY TIMELINE

4.1 Time to Complete Accrual

The approximate time to complete study enrollment is expected to be 12 months.

4.2 Expected Duration of Participation

The expected duration for maternal participants is approximately 24 weeks, not including the screening window. Infants will be followed for a full year after birth; therefore, follow-up after enrollment is approximately one year and 4 months. Maternal study data will be collected from the participant and/or her medical records through the Post-Treatment (SVR12) Visit (V6). Maternal participants who experience adverse events (AEs) at the Post- Treatment Visit (V6) that are clinically significant or related to study product/participation will be followed beyond V6 until a clinically acceptable resolution or stabilization of the AE(s) is confirmed and documented. The follow-up may be done via phone as applicable. Similarly, infant study data will be collected through the 12-month follow-up visit (iV3). Infants who have AEs at the iV3 visit that are clinically significant or related to study product/participation and have not resolved or stabilized will be followed beyond iV3 until a clinically acceptable resolution or stabilization of the AE(s) is confirmed and documented. The follow-up may be done via phone as applicable.

5 STUDY POPULATION

5.1 Selection of the Study Population

5.1.1 Recruitment and Retention

Recruitment will take place at multiple study sites and according to the site's recruitment SOP. All recruitment materials and procedures will be approved prior to use by the site/local IRB/REB.

The importance of retention will be stressed to the participant at each visit as part of protocol adherence counseling and as per the site's retention SOP. Once a participant is enrolled, the study staff will make every effort to retain the participant in follow-up. If a participant is lost to follow-up or is discontinued from the study prior to the completion of the final maternal visit evaluating SVR12, then an additional/replacement participant will be enrolled into the study from any participating site.

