2.2 Rationale

Pregnancy is a critical window of opportunity for HCV screening and **treatment.** Pregnancy may be the ideal time to provide HCV treatment due to enhanced maternal investment in neonatal health outcomes as has been demonstrated for maternal HIV infection. A meta-analysis of adherence to antiretroviral therapy during and after pregnancy showed a statistically significant difference in adherence during pregnancy (75.5%) compared to the postpartum period (53.0%)²³. Recently the CDC and the USPSTF have recommended that pregnant women be screened for HCV during each pregnancy, so this may be the time when many women learn that they have chronic HCV.24,25 In a retrospective cohort study of 369 pregnant women who were HCV seropositive at our institution from 2009 to 2012, 285 (77%) were referred to hepatology for postpartum treatment, but only 71 (25%) attended the consultation and only 6 (1.6%) were treated in the first year postpartum²⁶. Furthermore, in an ongoing study of postpartum HCV treatment with SOF/VEL paired with medication-assisted treatment (MAT) at our institution, 6 (50%) of 12 enrolled participants were lost to follow-up prior to treatment completion²⁷. Thus, pregnancy may be the ideal period for enhanced HCV treatment adherence and engagement.

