2.4 Clinical Studies

2.4.1 Clinical Studies of Sofosbuvir/Velpatasvir for the Treatment of HCV

Approximately 1035 participants without cirrhosis or with compensated cirrhosis have been enrolled in several multicenter, Phase 3 trials to assess the efficacy of treatment with SOF/VEL for 12 weeks in patients with genotypes 1, 2, 3, 4, 5, and 6 chronic HCV in ASTRAL-1, ASTRAL-2 and ASTRAL-3 (Table 2). ASTRAL-1 was a randomized, double-blind, placebo-controlled trial that evaluated 12 weeks of treatment with SOF/VEL compared to placebo in participants with genotype 1, 2, 4, 5, or 6 infection without cirrhosis or with compensated cirrhosis³¹. ASTRAL-2 was a randomized, open-label trial that evaluated 12 weeks of SOF/VEL compared to 12 weeks of SOF plus ribavirin in subjects with genotype 2 infection³². ASTRAL-3 was a randomized, open-label trial that evaluated 12 weeks of SOF/VEL compared to 24 weeks of SOF plus ribavirin in genotype 3 infection³². Approximately 40% (over 400 participants) in these trials were women. There were no on-treatment virologic failures reported (persistent viremia while actively taking SOF/VEL), however 13 (1%) participants experienced virologic failure after treatment or relapse, most commonly among participants with genotype 3 infection. Another 12 (5%) participants failed to achieve SVR12 due to non-adherence, adverse reaction (n=2) or another reason for treatment interruption (Table 2).

Table 2: Virologic outcome of a 12-week course of SOF/VEL for the treatment of HCV infection in participants without cirrhosis or with compensated cirrhosis from ASTRAL-1. ASTRAL-2. and ASTRAL-3

geno-	Total n	SVR12	SVR12	on-treatment	after-treatment	Other
type		n	rate	virologic failure	virologic Failure	
1	328	323	98%	0	2 (1%)	3 (1%)
2	238	237	100%	0	0	1(<1%)
3	277	264	95%	0	11(4%)	2 (1%)
4	116	116	100%	0	0	0
5	35	34	97%	0	0	1 (1%)
6	41	41	100%	0	0	0

Safety

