7.5 Follow-up Procedures for Participants Who Permanently Discontinue Study Medication

Participants will be permanently discontinued from study medication for significant laboratory abnormalities or adverse events as outlined in section 9.3 and 9.4, or if they choose to discontinue study medication. The participant will be asked to continue in the study and complete applicable remaining study procedures for safety purposes, including maternal and infant study procedures. To reduce burden on the participant and prevent lost to follow-up, in person visits can be converted to telephone visits for the collection of adverse events and safety labs can be collected from the medical record as performed for standard of care.

Participants who are permanently discontinued from study medication will be instructed to return any remaining study medication. All protocol-specified study procedures will continue for safety except the following:

- Provision of study medication
- Provision of medication use/adherence counseling

The following procedures will be performed at the visit at which study medication use is permanently discontinued or at the next in person visit:

^{**}If HCV RNA is detectable at iV1, iV2 or iV3, then HCV genomic deep sequencing should be collected/stored. If infant is at high-risk of HCV perinatal transmission, then an additional sample can be drawn at the time of the HCV RNA test and stored until the HCV RNA test has resulted. If the HCV RNA result is undetectable, then the stored sample will be discarded.

^{***}An age-appropriate physical exam is required during the infant study visit. However, if the infant participant misses a visit, then an age-appropriate physical exam may be abstracted from the medical records if it occurs during the visit window.

- HCV viral load
- HCV genomic deep sequencing (collected and used as necessary) or stored sample for future use, as applicable
- Medical history review
- Concomitant medication review
- Record/update AEs
- Modified physical examination including vital signs, if indicated.

If an in person visit is not possible, applicable information may be retrieved from their routine care medical chart as appropriate.

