10 STATISTICAL CONSIDERATIONS

10.1 Overview and Summary of Design

This is a Phase 4, single-arm, open label cohort study of treatment for chronic HCV infection during pregnancy in approximately 100 HCV-infected pregnant women receiving a 12-week (84 day) course of SOF/VEL and their infants. Maternal participants will be considered evaluable if they have a HCV viral load result at the Post-Treatment visit (V6) or have a HCV viral load drawn from clinical care that occurs during or any time after the V6 visit window. Pregnancy and neonatal outcomes will be compared to a historical cohort of pregnant women with active HCV from each of the participating study sites.

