10.3 Sample Size

The sample size of approximately 100 participants was chosen in order to determine if a clinically meaningful difference exists between the prospective treatment cohort and the historical or published comparison groups regarding preterm birth <37+0 weeks' gestation and maternal SVR12.

To estimate the sample size required for maternal SVR12, a baseline SVR12 of 97% was used. This estimate was based on a 30% prevalence of HCV genotype 3 among young persons and the published rate of SVR12 for all genotypes³³. For maternal SVR, using an exact binomial test with a nominal 10% one-sided significance level will have 82% power to detect the difference between the Null hypothesis proportion, π_0 of 97% (published rate of SVR12 with SOF/VEL) and the Alternative proportion, π_1 , of 92% when the sample size is 100.

For the primary neonatal outcome of preterm birth <37+0 weeks' gestation, using Fisher's exact test a sample size of 100 will identify a difference of 13 percentage points in preterm birth rates (80% power 2-sided alpha = .05). The published preterm birth rate of 23% among HCV+ pregnant women at the University of Pittsburgh was used to calculate this estimate³⁴.

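### SVR12 is fixed as a rate among women with an observed post-treatment HCV RNA; treated women without one are replaced and not accounted for, which can hide a shortfall against 97%

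*Protocol*

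**What the plan says.** Three places in the protocol set the SVR12 denominator.

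- Section 5.1.1 provides an additional or replacement participant for any woman who is "lost to follow-up or is discontinued from the study prior to the completion of the final maternal visit evaluating SVR12".
- Section 7.4.4 covers the woman with no HCV RNA at V6 and none in her medical record from the V6 window or later: "then the participant is NOT evaluable and will be replaced with a new participant".
- Section 10.1 carries this into the statistical section. Its definition begins "Maternal participants will be considered evaluable if they have a HCV viral load result at the Post-Treatment visit (V6" and goes on to admit a clinical-care result from the V6 window or any time afterwards.

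Section 10.3 sizes the comparison: "using an exact binomial test with a nominal 10% one-sided significance level will have 82% power", with 97% as the null, 92% as the alternative and 100 women. Section 10.4.4 repeats the one-sided exact binomial test against 97%. Both sections cite the 97% to a published systematic review and meta-analysis (reference 33).

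No section counts a treated woman without an RNA as a non-responder, reports her separately, or says how many replacements are expected.

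**The concern.** The test is built to detect a cure rate below 97%. Removing women with no result from the denominator is harmless only if they were cured as often as the women who returned. The protocol gives reasons to doubt that.

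- Section 9.3 lists inability or unwillingness to comply as a reason to stop study medication, and Section 9.6 lists it as a reason for withdrawal from the study.
- For women who stop study medication, Section 7.5 says that "in person visits can be converted to telephone visits for the collection of adverse events". It also calls for an HCV viral load at discontinuation or the next in-person visit, but a result taken before the V6 window does not make a woman evaluable.
- V6 comes 12 weeks after a 12-week course that starts at 20+0 to 30+0 weeks, which is 44 to 54 weeks from dating. It is therefore postpartum for practically everyone. Section 2.2 describes weaker engagement postpartum: antiretroviral adherence of 53.0% against 75.5% in pregnancy, and a postpartum SOF/VEL study in which "6 (50%) of 12 enrolled participants were lost to follow-up prior to treatment completion".

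If the lost women are more often failures, the observed-RNA rate is too high and the test becomes less likely to flag a real shortfall. A reader of the result would not know how many treated women stand behind the 100 reported.

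**Working it through.** **Inputs.** From Sections 10.3 and 10.4.4: null 97%, alternative 92%, n = 100, one-sided exact binomial test at a nominal 10%. From Table 2 in Section 2.4.1: genotype totals, SVR12 counts, relapses and the Other column. The protocol gives no loss rate for this trial and no SVR12 among women lost, so both are assumed below.

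**The plan's own figure.** Reject when failures ≥ 6 of 100 (SVR12 ≤ 94/100).

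- Exact alpha = P(SVR12 ≤ 94 | 97%) = 8.1%. The next rule, ≤ 95/100, has alpha 18.2% and is not admissible.
- Power = P(SVR12 ≤ 94 | 92%) = 82.0%. The stated 82% reproduces.

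**Effect of informative loss.** Hold the true all-treated rate at 92%. Let L be the fraction without an RNA and s the SVR12 among them. Then

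observed-RNA rate = (0.92 − L × s) / (1 − L)

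and power = P(SVR12 ≤ 94 of 100) at that rate.

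| L | s | Observed-RNA rate | Power |
|---|---|---|---|
| 0% | – | 92.0% | 82% |
| 5% | 70% | (0.92 − 0.035)/0.95 = 93.2% | 69% |
| 10% | 70% | (0.92 − 0.07)/0.90 = 94.4% | 48% |
| 15% | 70% | (0.92 − 0.105)/0.85 = 95.9% | 23% |
| 10% | 92% | (0.92 − 0.092)/0.90 = 92.0% | 82% |

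The last row is loss unrelated to outcome: no bias and no loss of power.

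**A single result.** 97 of 100 evaluable gives p = P(X ≤ 97 | 100, 97%) = 0.58. If three women had been replaced and all three are counted as failures, the result is 97/103 = 94.2% and p = 0.09, below the 10% level. Three women absent from the reported denominator can change the conclusion.

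**The benchmark side.** Table 2 sums to 1035 patients, 1015 with SVR12, 13 relapses and 7 Other. The text describes the non-virologic failures as "participants failed to achieve SVR12 due to non-adherence, adverse reaction (n=2) or another reason for treatment interruption", and Table 2 keeps the Other patients in the denominator as non-SVR. With them the rate is 1015/1035 = 98.1%; without them it is 1015/1028 = 98.7%. The choice of basis moves the Table 2 rate by about 0.7 points, so the bias that matters here is on the trial side.

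**The cost of the opposite rule.** Suppose the true SVR12 is 97% whether or not a woman is lost, and missing RNA is scored as failure in the first 100 enrolled.

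- At 5% loss the scored rate is 0.97 × 0.95 = 92.2%, and the test flags a shortfall 81% of the time.
- At 10% loss the scored rate is 0.97 × 0.90 = 87.3%, and it flags one 99% of the time.

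**The case against.** Much can be said for the plan, and it limits the point in five ways.

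- *A reader might call this a completers-only rate.* It is not. A woman who stops the drug early but has an RNA at V6, in its window or at any later time is counted, including as a failure.
- *A reader might infer that the 97% comes from trials that scored non-completers as failures.* That is shown only for the phase 3 trials in Table 2. The 97% is cited to a meta-analysis whose missing-data rule the protocol does not give.
- *A reader might say that Sections 7.5 and 9.6 steer failures out of the study.* Their stated aim is the reverse. Section 7.5 asks women who stop to stay in the study and allows telephone visits to prevent loss. Section 9.6 asks for every reasonable effort to continue follow-up. Some loss may still occur, but it is not designed in.
- *A reader might infer that replaced women also leave the preterm-birth and safety analyses.* No section says so. Sections 10.4.2 and 10.4.3 set no such restriction, and Section 7.4.3 has delivery records reviewed for all participants.
- *The loss rates are assumed.* The 6 of 12 in Section 2.2 comes from treatment given postpartum, and the protocol cites it to argue that retention is better in pregnancy. With small or non-informative loss, little or nothing changes.

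Missing-equals-failure as the only headline would also let retention drive the test, as the last calculation shows.

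All of this stands. It does not remove the core: the protocol itself fixes replacement and an observed-RNA denominator, and gives the replaced women no place in the SVR12 result.

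**Conclusion.** The point holds in limited form. Sections 5.1.1, 7.4.4 and 10.1 make the primary SVR12 a rate among women with an observed post-treatment RNA, and the treated women who were replaced are not accounted for. This is stated in the protocol, so it is not merely a detail awaiting an SAP.

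The size depends on loss that nobody can yet know. Power against a true 92% goes from 82% to 69%, 48% or 23% at 5%, 10% or 15% loss if 70% of the lost women were cured. It stays at 82% if loss is unrelated to outcome. The direction is clear if loss is linked to non-adherence or early stopping: the rate is too high and a shortfall is harder to see.

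A mismatch of basis with the 97% benchmark remains possible but cannot be established from the protocol. Severity: should be fixed.

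**What to change.** Keep replacement, which protects precision, and add the following to the protocol or the SAP.

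1. Retain every woman who took at least one dose in the reported SVR12 results, and state how many were replaced and why.
2. Report the all-treated rate, with missing RNA as non-SVR and an exact confidence interval, beside the observed-RNA rate. Show a sensitivity range between the two by varying the SVR12 assumed for women without an RNA.
3. State which basis any comparison with 97% uses. Do not conclude from the observed-RNA rate alone that SVR12 is no lower than 97%.
4. State that V6 evaluability applies only to SVR12, so that delivery, maternal safety and infant outcomes include all treated women with known outcomes.

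The cost is wording and a small amount of extra reporting, with no new data. The all-treated figure will be less favourable and mixes retention with cure, which is why both rates should be shown and neither should stand alone.
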